6.5 STATISTICAL ANALYSIS

Intention-to-treat analysis regardless of dropout or study adherence is the primary analytic strategy. Primary and secondary continuous outcomes will be analyzed via linear repeated measures mixed models for testing of Group X Time interaction, with covariate adjustment over baseline and 4 weeks to characterize the intervention effects. In addition, outcomes at 5-8 weeks will identify and characterize any residual effects of the intervention during the washout phase and will be analyzed with respect to the intervention changes to determine the time course, if any, of residual effects. Covariates selected *a priori* based on the literature include age, sex, macronutrient intake, energy intake, and habitual physical activity level; other potential confounders identified at baseline may be added as required. A mediation analysis will be conducted via the PROCESS macro for SPSS version 2.13.2 to determine the indirect effect of dietary change on objective and subjective outcomes mediated by hypothesized beneficial alterations in the gut microbiota, while accounting for any potentially direct effects of EVOO.

[figure not shown]

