The treatment groups for both participants with UC and healthy controls will be instructed to modify their current dietary intake by replacing a portion of their fat intake with extra virgin olive oil (EVOO) over a 4-weeks. We will aim to replace all free fats or fats added into meal preparation which includes but is not limited to cooking oil, fat spreads, butter, and oil based dips and sauces. For the purposes of this study, we will aim to ensure that energy intake between participant's usual diet and the intervention remains the same. As such, average energy contributions of free fats in the diet will be calculated, which will then be converted to the quantity of EVOO required to be consumed daily. Kitchen weight scales and marked bottles will be used to assist estimating the participant's daily requirement. The study dietitian will provide information on strategies to incorporate the oil into the participant's daily meals and a checklist for daily intake to assist with the behaviour change. If the participant is fasting for any reason during the study, the intervention will resume once the participant is able to consume meals again. No top ups from previous days will be required. For participants with shared meal preparation responsibilities in the household, additional bottles of EVOO will be provided. The EVOO used for this study will be Australian produced EVOO currently available for sale as a food item in accordance with Australian food regulations and will not be a special product or formulation. Upon completion of the 4 weeks of the intervention, all remaining EVOO bottles will be collected and participants will be requested to return to consuming their regular diet. During this 4-week washout period, participants will resume their usual intake of free fats to identify any sustained effects of the intervention.

Both during active intervention and the washout period, participants will be requested to maintain all their daily activities including physical activity, sleep and exercise. All of the documentation of changes in health care, habitual exercise or diet noted for the control group below will also be recorded in the intervention group.

Control Group: Usual Care

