9. OUTCOMES AND SIGNIFICANCE

9.1 OUTOMES

Table 2 illustrates the COLONIC study primary and secondary outcomes. Table 2 illustrates the outcomes that will be assessed and the time points at which each outcome will be assessed (Baseline, 4 weeks, 8 weeks).

Primary Outcomes	Time Point
Disease Activity for Ulcerative Colitis Partial Mayo Score for Ulcerative Colitis	Baseline, 4 weeks, 8 weeks
Microbiome Dysbiosis Evaluation of gut bacterial profiles. Participants will be required to produce a stool sample into a plastic bag, ensuring no fluid or urine comes in contact with the sample. Participants will be provided with a collection kit with instructions. The fecal sample will be stored at the University of Sydney freezers at -80°C if produced onsite, or stored in participant's freezers then transported to the University of Sydney during the clinic date. It will then be transported to Medlab Clinical ([name]) in batches where they will be stored at -80°C and then analyzed	Baseline, 4 weeks, 8 weeks

once there are enough samples to make the run financially viable (approximately every 10 samples).
	

Secondary Outcomes
	

Nutrition 3-day weighted food records, 1 Month Retrospective Food Frequency Questionnaire (FFQ), Probiotic foods and nutraceutical inventory, Risk of Malnutrition via the Mini Nutritional Assessment (MNA) Diet quality as determined by the CSIRO Diet Index Polyphenol content of the diet as determined by FoodWorks Oleic acid intake as determined by FoodWorks Diet Inflammatory Index (DII) Plasma Oleic Acid levels Faecal SCFA content Plasma Hydroxytyrosol sulfate and Tyrosol as determined by ultra-HPLC-ESI-MS/MS Self-reported symptoms diary for food intolerances and adverse reactions Food Choice Questionnaire Food Related Quality of Life Questionnaire for IBD (FR-QoL-29)
	
Baseline, 4 weeks, 8 weeks

Anthropometry Waist, upper-arm and calf circumferences, height, weight, Resting Heart Rate
	Baseline

Body composition Whole body and regional lean and adipose tissue, Bone density in the lumbar spine and hip. Dual-energy X-ray absorptiometry (DXA)
	Baseline

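### Section 6.5 leaves open whether week-4 diet and activity enter the primary intention-to-treat model as covariates: week-4 values can bias the effect, baseline main effects do nothing, and the free Group x Time test forgoes precision

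*Protocol*

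**What the plan says.** Protocol Section 6.5 sets the principle: "Intention-to-treat analysis regardless of dropout or study adherence is the primary analytic strategy". Continuous outcomes go into "linear repeated measures mixed models for testing of Group X Time interaction", "with covariate adjustment over baseline and 4 weeks to characterize the intervention effects". The covariates named in advance "include age, sex, macronutrient intake, energy intake, and habitual physical activity level; other potential confounders identified at baseline may be added as required". No visit is attached to any of them.

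Section 6.2 defines the intervention as "replacing a portion of their fat intake with extra virgin olive oil (EVOO) over a 4-weeks", and adds that "we will aim to ensure that energy intake between participant's usual diet and the intervention remains the same".

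Section 9.1 lists diet as a secondary outcome at baseline, 4 and 8 weeks, including "3-day weighted food records, 1 Month Retrospective Food Frequency Questionnaire (FFQ)" and "Oleic acid intake as determined by FoodWorks". The synopsis also counts macronutrient intake among the secondary outcomes. Accelerometer-measured activity is repeated at the same three visits, and so is the Partial Mayo Score, a primary outcome.

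Section 6.5 then plans a mediation analysis in which dietary change is the exposure.

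**The concern.** One family of variables has three roles: what the intervention changes, a secondary outcome, and a covariate in the primary model. An intention-to-treat effect is the effect of assignment through every path. Conditioning on intake measured after assignment removes any part of the effect that runs through intake. It can also open a non-causal path if something unmeasured drives both intake and symptoms. Departure from the planned swap is a form of adherence, which this analysis principle is meant not to condition on.

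Two further points sit in the same passage. The free Group x Time test does not use baseline Partial Mayo efficiently, which matters with 12 completers planned per arm. And the closing clause of the covariate sentence allows variables to be added after baseline data are seen, with no rule for choosing them.

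**Working it through.** **Inputs from the protocol (Section 6.4).** Target difference 2 points; pooled SD 1.6; 12 per UC arm; alpha 0.05 (taken as two-sided); power 0.80 (the protocol labels 0.8 as beta). Table 1 SDs for the Partial Mayo study are 1.2 at baseline and 2.0 after the diet.

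**Assumed, because the protocol gives no figure.** Baseline to week-4 correlation r of 0.3 to 0.8; a between-arm intake shift of 0 or 1 SD at week 4; an intake effect of 0, -0.5 or -1 point per SD.

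**1. The plan's own figure.** 2/1.6 = 1.25. The two-sample t-test needs 11.09 per group, so 12, with 83.3% power. The stated 12 reproduces. That calculation has no covariates, so it does not settle this point.

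**2. Baseline-only covariates.** With two visits and complete data, write Y(i,t) = a + b·g + c·t + d·g·t + k·X(i) + person effect + error. Week 4 minus baseline gives D(i) = c + d·g + error. X(i) has gone, and d is the difference in mean change between arms. Fitting the model with and without baseline-only main effects confirmed this: the estimate was unchanged to rounding error and the standard error was the same to at least four decimals. On this reading the adjustment is inert for the primary contrast.

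**3. Week-4 values as time-varying covariates.** Replace X(i) by intake M(i,t) with coefficient m. Then D(i) = c + d·g + m·[M(i,4) - M(i,0)] + error, and the fitted d is the total effect minus m × (intake shift between arms).

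| Intake shift | Effect per SD of intake | Fitted effect (true total -2) |
|---|---|---|
| 0 | any | -2.0 |
| 1 SD | 0 | -2.0 |
| 1 SD | -0.5 | -2 - (-0.5 × 1) = -1.5 |
| 1 SD | -1 | -2 - (-1 × 1) = -1.0 |

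Simulation of 4,000 trials at 12 per arm, adjusting for week-4 intake, gave -1.51 and -1.00 for the last two rows. With a 1 SD shift, no effect of intake, but an unmeasured common cause of intake and score, the estimate moved the other way, to -2.27. Adjusting for baseline intake gave about -2.0 in every scenario. With a 1 SD shift and no mediated path, week-4 adjustment also raised the empirical standard error from about 0.59 to 0.69.

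**4. Free Group x Time against baseline adjustment.** SD of change = √(s1² + s2² - 2·r·s1·s2). Baseline-adjusted residual SD = s2·√(1 - r²). The standard error is either SD × √(2/12).

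| SDs (s1, s2) | r | SE, change | SE, adjusted | Ratio | Power, change v adjusted |
|---|---|---|---|---|---|
| 1.6, 1.6 | 0.3 | 0.773 | 0.623 | 1.24 | 70% v 86% |
| 1.6, 1.6 | 0.5 | 0.653 | 0.566 | 1.15 | 83% v 92% |
| 1.6, 1.6 | 0.7 | 0.506 | 0.466 | 1.08 | 96% v 98% |
| 1.6, 1.6 | 0.8 | 0.413 | 0.392 | 1.05 | above 99% for both |
| 1.2, 2.0 | 0.3 | 0.816 | 0.779 | 1.05 | 65% v 69% |
| 1.2, 2.0 | 0.6 | 0.653 | 0.653 | 1.00 | 83% v 83% |

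In the last row the regression slope of week 4 on baseline is 0.6 × 2.0/1.2 = 1, so the two analyses coincide.

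**The case against.** The strongest reply is that Section 6.5 never says post-randomisation intake is used. The phrase about baseline and 4 weeks can describe the analysis window, since the next sentence turns to weeks 5 to 8. The covariates are chosen in advance, activity is described as habitual, and further confounders are those found at baseline. This stands: a reader might infer that the estimate is biased, but the documents support only that it may be, if week-4 values are used and differ between arms. The reply does not rescue the sentence, because on the baseline reading main-effect adjustment does nothing to the two-visit contrast.

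The isocaloric design also counts against a large bias. The planned change is in fat type, while total energy is meant to stay level. But that is an aim rather than a guarantee, and Section 6.5 does not say whether macronutrient intake means totals or includes fat subtypes.

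Three other inferences fail:

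- **Baseline Partial Mayo is left out.** It is not; it is the first repeated outcome. The free Group x Time test is valid, and the issue is efficiency only.
- **The covariate count wrecks power.** A single-visit regression with seven unrelated covariates does fall from 84% to 67% power in simulation, but that is not the stated model.
- **Energy and macronutrients are collinear.** This inflates the intake coefficients and barely touches the treatment contrast: single-visit power was 66.5% with seven independent covariates and 65.6% with one a near-sum of three others.

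Finally, details of covariate handling often belong in an SAP. Here, however, the protocol itself names the covariates and leaves the list open.

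**Conclusion.** The point holds in a conditional form. As written, the adjustment for intake and activity is either inert (baseline main effects) or a threat to the intention-to-treat estimand (week-4 values). In the second case a true -2 points becomes about -1.5 to -1.0 under an assumed 1 SD shift carrying 0.5 to 1 point per SD. It stays at -2.0 if the arms do not differ in intake, and can be overstated (-2.27 in one assumed scenario) if there is an unmeasured common cause. The shift and the strength of the path are assumptions; the protocol gives neither.

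The precision point is secondary. The standard error is 5% to 24% larger than necessary for r from 0.8 to 0.3 at equal SD 1.6, and 0% to about 5% larger over the same range with Table 1's SDs. The open covariate clause is a fault on any reading, because it permits the primary model to be chosen from the data.

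**What to change.** In Section 6.5:

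1. State that no intake or activity value measured after randomisation enters the primary model, and that week-4 intake is used only to describe adherence and in the mediation analysis.
2. Analyse Partial Mayo either with its baseline value as a covariate and only follow-up scores as outcomes, or with a mixed model that constrains the arm means to be equal at baseline. Adjust for sex, which is a stratification factor, and for prespecified baseline covariates such as age.
3. Replace the clause allowing further confounders with a closed list.

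The cost is a few sentences of analysis text and one degree of freedom for the baseline covariate. No new data are needed, and the sample size does not change.

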7. ETHICAL CONSIDERATIONS

7.1 RECRUITMENT AND SELECTION OF PARTICIPANTS

Potentially eligible participants will be recruited from the greater Sydney area. The study will be advertised broadly via flyers distributed through doctor's surgeries, gastroenterologist clinics, and offices of health care facilities. The study will also be advertised via social media (e.g., Facebook and Twitter), university intranet and websites, and local radio. Permission will be obtained from each of these sites prior to advertising the study. All advertising material will have the contact number and email address of our research team on it, and interested participants will contact us directly if they wish to hear more about the study and wish to schedule a telephone screen for eligibility. We will avoid real or perceived coercion by indicating in the recruitment letters of invitation and telephone screen that this is completely voluntary and will in no way influence their health care and treatment. The screening and initial contact will be done by the student overseeing the study. We will not be contacting people by email addresses without their permission after initial telephone screening and will not be sending letters or calling people directly who have not previously given us permission to do so or have called us in response to one of our recruitment materials.

Potentially eligible participants will undergo a two-stage screening process which includes a telephone screen and in-person physical and health screen. Both participants with UC and healthy controls recruited will undergo the same screening process as illustrated in Figure 1.

Figure 1. COLONIC Screening Procedure

Telephone screen

Initial screening	
Presence of Inflammatory Bowel Disease	Participant confirms that have been diagnosed with Ulcerative Colitis (UC) at least 3 months or greater in duration.
(only for participants with UC)	Confirmation of disease activity via the Partial Mayo Scoring Index for UC
Confirmation of eligibility	Participants confirm that they do not meet any of the exclusionary criteria.
Medical history and medication review	Review of medical history and current medications and/or therapies.
Medical contact details	Contact details of treating general practitioner (GP) and gastroenterologist are collected.
Confirmation of inclusion criteria with GP and relevant specialists	A letter is sent to the participant's GP and relevant specialists for confirmation of inclusion criteria and to rule out any exclusionary study criteria, unstable diseases, or contraindications to participation in the study.

Participants who meet the study criteria as assessed during telephone screening. Those deemed to be eligible and are still interested in participating will be requested to attend an in person physical and health assessment at the University of Sydney Cumberland Campus C Block Clinic at a nominated date. Prior to any assessments at the clinic, participants will be briefed on the Participant Information Statement (PIS) with a copy provided to the participant. This will be followed by a written, witnessed, and informed consent on participating in the COLONIC Study.

Assessments will be completed over 2 days, spread at least between 7 days, with the first assessment to include a physician health screen, a variety of questionnaires and physical performance measures. Upon completion of this first assessment, participants will be fitted with an Axivity AX3 accelerometer to wear over a 7-day period. Participants will also be provided with instructions on completing a 3-day food diary and stool collection kit for home collection. All provided samples and diaries will be collected during the second assessment.

In-person Physical and Health screen

This screening takes place over two days (at least 7 days apart). Findings obtained from the assessments over the 2-day period may make the person ineligible for participation or placed on-hold for further investigation. Note that day 2 of the assessment will be done while the participant is in a fasted state.

DAY 1 - Physical and Health Screen

Physician screening and exercise stress test	Physician health screen, resting electrocardiogram (ECG), exercise stress test with ECG.
Inflammatory bowel disease activity (only for participants with UC)	UC disease activity including subjective physician assessment, via the Partial Mayo Scoring Index for UC.
Muscle strength	1 repetition maximum tests for the chest press, seated row, triceps push down, lateral pull-down, leg press, leg extension, leg flexion, hip abduction and hip extension.
Muscle power	Chest press, seated row, triceps push down, lat pull-down, leg press, leg extension, leg flexion, hip abduction and hip extension.
Questionnaires	Baseline measures: Demographic, physical activity and sedentary behaviour, nutritional status, food related questionnaires, food choice questionnaires, and functional status questionnaires.
Physical activity and sleep assessment	Participants will be fitted with an Axivity AX3 accelerometer to wear for 7 days and provided with a sleep diary. Paffenbarger Physical Activity Questionnaire will be completed in person.

DAY 2 – Physical and Health Screen (Participants arrive in a fasting condition)

Stool sample collection	First bowel motion of the day to be collected. Can be completed either at home using the supplied collection kit or in clinic prior to assessment 2.
Anthropometric measures and body composition	Weight, height, waist circumference, DXA scan. DXA assessments to measure bone mineral density will be completed at baseline only for all participant groups.
Blood test	Lipopolysaccharide (LPS), C-reactive protein (CRP), tumor necrosis factor and interleukins 1, 6, 10 and 12, full blood count. Save serum and plasma for other markers.
Collection of forms provided at assessment 1	Review of electronic and/or paper based 3-day food diary and sleep diary. Activity
Questionnaires	Inflammatory Bowel Disease (IBD) Questionnaire, Depressive Symptoms will be assessed via the Hospital Anxiety and Depression Scale (HADS) and Patient Health Questionnaire (PHQ-9), fatigue will be assessed via the IBD Fatigue Scale.

Individuals deemed eligible as assessed during in-person physical and health screen, and who are still interested to participate, are enrolled and randomised into the study.

Figure 2 illustrates an overview of the study flow from screening of participants until completion of the study.

Figure 2. COLONIC Study Scheduling

2 – 3 Weeks	Stage 1 Screen	Telephone Screen (Duration ~60 minutes)
	Participant Information Sheet & Consent Form	
	Baseline Clinic Visit 1	
In person physical and health screen (duration ~4-5 hours)
 
 - Participant Information Sheet (PIS) & informed consent - Questionnaires (demographic, nutrition status) - Physician Screen - Functional Assessment - 3-day Weighted Food Diary Instruction - Stool Collection Instructions - 7-day Axivity Monitor Attachment 
Location: The University of Sydney, Faculty of Health Sciences, Lidcombe

2 Weeks	Baseline Clinic Visit 2 (must be at least 8 days after Clinic 1)	
In person physical and health screen (duration ~5-6 hours)
 
 - Fasted assessments - Anthropometry - Collection and review of assessment 1 forms 
Location: The University of Sydney, Faculty of Health Sciences, Lidcombe

	
Randomisation into 1 of 4 Groups (UC Usual Care, UC Intervention, Control Usual Care, Control Intervention)
	
4 Weeks	Intervention (Week 1-4)	
Intervention: Replacement of usual free fats with the study fats
 
Usual Care: Maintain all usual daily activities
 
Weekly teleconference for all study groups (duration 15-20 minutes) Review new symptoms, changes to current therapy, lifestyle, visits to a healthcare professional

2 Weeks	Mid-Point Assessment (Week 5, over 2 days)	
Repeat a portion of assessments in Clinic Visit 1 and Clinic Visit 2
 
 - Fasted assessments - Nutrition assessment & food diaries - Stool collection - Questionnaires 
Location: The University of Sydney, Faculty of Health Sciences, Lidcombe

4 Weeks	Washout Period (Week 6-9)	
Intervention 1 and 2: Collection of all unused study fats, resume usual daily behaviour prior to study
 
Usual Care: Maintain all usual daily activities
 
Weekly teleconference for all study groups (duration 15-20 minutes) Review new symptoms, changes to current therapy, lifestyle, visits to a healthcare professional

2 Weeks	Final Assessment Clinic Visit 1	
In person physical and health screen (duration ~3-4 hours)
 
 - Physician review (as required) - Questionnaires (food intake, IBD symptoms, affect) - 3-day Weighted Food Diary Instruction - Stool Collection Instructions - 7-day Axivity Monitor Attachment 
Location: The University of Sydney, Faculty of Health Sciences, Lidcombe

	Final Assessment Clinic Visit 2 (must be at least 8 days after Clinic 1)	
In person physical and health screen (duration ~2-3 hours)
 
 - Fasted assessments - Anthropometry - Collection and review of assessment 1 forms 
Location: The University of Sydney, Faculty of Health Sciences, Lidcombe

End of Study Participation		

During each week of the study the participants in both the intervention and control groups will be provided with a questionnaire to complete which will be used to assess their health status and reporting of events throughout the study period. The Partial Mayo Scoring Index for Ulcerative Colitis will be incorporated in these weekly health checks to subjectively assess disease activity and allow participants to report any changes to their symptoms.

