4. AIMS

1. To conduct the first RCT of the effects of chronic extra virgin olive oil consumption on the human gut microbiota in both healthy and diseased states
2. To conduct the first RCT of the impact of extra virgin olive oil on the expression of UC in those with mild-moderate disease states
3. To assess the relationship between inflammation, gut microbiota changes and UC symptoms in response to a short term dietary prescription
4. To investigate the course of the alteration and persistence of the responses to dietary change by characterizing the gut microbiota and biological markers of the disease during the intervention period and any sustained or residual effects 4-weeks post-intervention.

Primary Hypotheses

1. Replacement of dietary fats with extra virgin olive oil will positively influence disease activity scores and disease symptoms
2. Dietary fat replacement will modulate the gut microbiota profile of those with UC and healthy controls.
3. Distinct changes in the gut biota will occur between participants with UC and healthy controls once exposed to the diet intervention, indicating the importance of gut microbiota in modulating disease outcomes.
4. The impact of short term dietary changes has longer term effects post cessation of the diet.

Secondary aims of the study will be to determine the effect of extra virgin olive oil on inflammatory markers of UC and quality of life measures, and characterization of dietary strategies in individuals living with UC. Adherence to the intervention protocol, weekly health status and adverse events also constitute secondary study outcomes.

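### Symptom scores and blood markers are taken at visits at least a week apart, and the spacing differs between instruments and between baseline and final assessment

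*Protocol*

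**What the plan says.** **Baseline (section 7.1).** Day 1 includes "UC disease activity including subjective physician assessment, via the Partial Mayo Scoring Index for UC". Day 2, attended fasting, lists the blood tests, the stool sample, and "Inflammatory Bowel Disease (IBD) Questionnaire, Depressive Symptoms will be assessed via the Hospital Anxiety and Depression Scale (HADS"), together with the PHQ-9 and the IBD Fatigue Scale. The text on spacing reads "This screening takes place over two days (at least 7 days apart"), whereas Figure 2 reads "Baseline Clinic Visit 2 (must be at least 8 days after Clinic 1"). Section 6.2 and Figure 2 place randomisation after the baseline assessment is complete.

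**Mid-point (Figure 2).** It is held over two days in Week 5, with no allocation of measures to days and no stated gap between them.

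**Final (Figure 2).** Visit 1 has "Questionnaires (food intake, IBD symptoms, affect") and gives out the stool instructions. The fasted assessments are at Visit 2, at least 8 days later. The Partial Mayo is not named at either final visit, although section 9.1 lists it at 8 weeks.

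**Stool.** Section 7.1 says "First bowel motion of the day to be collected. Can be completed either at home using the supplied collection kit". Section 9.1 allows home samples to be "stored in participant's freezers then transported to the University of Sydney during the clinic date".

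**Use of the data.** Aim 3 is "To assess the relationship between inflammation, gut microbiota changes and UC symptoms in response to a short term dietary prescription". Aim 4 concerns persistence of the response after the intervention. Section 6.5 plans a mediation analysis with the gut microbiota as mediator.

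**The concern.** Aim 3 and the mediation analysis link symptoms, inflammation and microbiota within a person. They are most informative when the three describe the same disease state. The protocol's own background describes UC as alternating between acute inflammation and remission, so readings a week apart cannot be assumed interchangeable.

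Two things follow. First, a lag between symptom score and blood sample weakens whatever association exists. Second, if the lag is zero at baseline and more than a week at the end, changes in symptoms and changes in biomarkers cover different intervals. That matters for Aim 4: if an effect fades during washout, questionnaires and blood would sample different points on the fade. The baseline Partial Mayo is also at least a week old at randomisation, which tends to make it a less informative baseline. This concerns what is collected and when, so a later analysis plan could not recover a same-day score that was never taken.

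**Working it through.** The plan's own figures here are the minimum gaps of 7 days (section 7.1 text) and 8 days (Figure 2). No sample-size figure depends on them. Setting the schedule side by side:

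| Assessment | Clinic Partial Mayo | IBDQ, HADS, PHQ-9, fatigue | Fasted blood | Stool |
|---|---|---|---|---|
| Baseline | Day 1 | Day 2 | Day 2 | listed under Day 2; home collection day open |
| Mid-point | day not stated | day not stated | day not stated | day not stated |
| Final | not named at either visit | symptom and affect questionnaires at Visit 1 | Visit 2 (fasted assessments) | instructions at Visit 1; collection day open |

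Two entries in the final row are inferences. The short labels in Figure 2 are read as IBDQ and HADS/PHQ-9 (fatigue is not named there), and blood is taken to belong to the fasted assessments, as it does at baseline.

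**Lags that follow**
1. Baseline Partial Mayo to blood, and to randomisation: at least 7 or at least 8 days, with no explicit upper limit.
2. Baseline questionnaires to blood: 0 days.
3. Final symptom and affect questionnaires to blood: at least 8 days.
4. Change in questionnaire-to-blood lag from baseline to final: at least 8 − 0 = 8 days. The questionnaires run from baseline Visit 2 to final Visit 1, while blood runs from Visit 2 to Visit 2.
5. Partial Mayo to stool: not determined. The kit is issued on Day 1 and home samples may be frozen, so the sample can fall anywhere between the two visits.

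**The weekly score.** Section 7.1 also puts the Partial Mayo into a weekly health check. On an unbroken 7-day cadence the nearest score is at most 7/2 = 3.5 days from any sample. Figure 2 shows weekly contact only in Weeks 1–4 and 6–9. If no check falls in Week 5, successive scores are about 14 days apart and the nearest is up to 14/2 = 7 days away.

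**Illustration only.** Assume a within-person correlation ρ between scores one week apart that decays as ρ^(gap/7). The documents give no ρ; 0.5 to 0.95 is assumed. The multiplier on a same-day correlation is:
- 8-day gap: 0.5^(8/7) = 0.45 to 0.95^(8/7) = 0.94
- 3.5-day gap: 0.5^(3.5/7) = 0.71 to 0.95^(3.5/7) = 0.97

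The range runs from serious to negligible, so it shows direction and not size.

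**The case against.** The strongest reply is the weekly Partial Mayo. The protocol describes it as running in each week of the study, so a score close in time to the samples is planned for much of follow-up. A reader might infer from the baseline schedule that Aim 3 and the mediation analysis must pair measurements from different weeks throughout. The documents do not support that: section 6.5 does not say which Partial Mayo reading is used, the mid-point (which carries the 4-week effect) has no stated split, and the Partial Mayo is not assigned to a final visit. Nor do they show that stool always comes a week after the score.

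The mitigation is incomplete, however. The checks are described for participants already in the intervention and control groups, so baseline is not clearly covered. Figure 2 shows no weekly contact during the mid-point or final assessment periods. The weekly score is called subjective and mentions no physician assessment, whereas Day 1 includes one.

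Other points stand. The interval between visits has a purpose (7-day accelerometer wear and a 3-day food diary). Entry requires stable medication for the preceding 4 weeks, which makes drift over one week less likely. Figure 2 is only an overview, and the questionnaire switch is read from brief labels. That switch bears on comparisons of baseline with final more than on the 4-week effect. Eight days satisfies both stated minimums, so that discrepancy is small.

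**Conclusion.** The point holds as a modest design weakness that is cheap to correct. Two facts are documented: the clinic Partial Mayo precedes blood and randomisation by at least 7 or 8 days at baseline, and the symptom and affect questionnaires move from 0 days before blood at baseline to at least 8 days before it at the end. The second rests on reading the Figure 2 labels as the baseline instruments.

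The effect is avoidable noise in Aim 3, Aim 4 and the mediation analysis, in a trial planning only 28 UC participants (section 6.4; 30 in section 6.2). It is not bias in the randomised comparison: the schedule is identical in both arms, and the baseline lag comes before allocation.

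Its size cannot be derived from the documents. A reader might take an assumed week-to-week correlation of 0.7 to 0.9 and conclude that 1/0.9² = 1.23 to 1/0.7² = 2.04 times as many participants are needed. That correlation is not in the protocol, and the formula applies to one cross-sectional correlation with a full lag. Aim 3 concerns change, and no lag is documented at 4 weeks.

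**What to change.** - Give IBDQ, HADS, PHQ-9 and fatigue at the fasted blood visit of every assessment: baseline, mid-point and final.
- Keep the full Day 1 Partial Mayo with its physician rating. Repeat the Partial Mayo at the fasted visit of each assessment, with the same components each time, so that a full 9-point score defines each time point. Repeating only the stool-frequency and bleeding items would shorten the primary scale on which the 2-point sample-size assumption rests.
- State how the mid-point measures are divided between its two days.
- Record the calendar date of each stool collection.
- Reconcile the 7-day and 8-day minimum gaps.

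The cost is a few extra minutes at Visit 2. The physician component must also be obtainable there; at the final assessment Figure 2 currently lists physician review only as needed, at Visit 1.
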